10.3.2 Secondary Endpoints

Changes in smoke intake and in nicotine intake indexed by salivary anabasine and salivary cotinine levels, assessed for participants still using NRT or EC at end of pregnancy and for 'dual users' or those who have reduced their smoking by 50% or more; 7-day point-prevalence abstinence self-reported at 4 weeks, end of pregnancy and at 3 months post-partum; self-reported prolonged abstinence at end of pregnancy and 3 months post-partum; use of NRT and EC throughout pregnancy; proportion of participants reporting adverse events and serious adverse events in each group; proportion of participants in each group reporting adverse events and serious adverse events for themselves or their infant at 3 months post-partum; birth and maternal outcomes.

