EC vs NRT in pregnancy: NRT has not shown efficacy in pregnancy, but there are reasons to expect that the barriers to NRT efficacy will be much less detrimental in the case of EC. Pregnant smokers seem to dislike oral NRT products but adherence to nicotine patch use is also very poor [14, 33] e.g. only 7% of women used patches for more than 1 month in the large UK trial [14]. Pregnant smokers may be finding patch use by itself unrewarding as the patches provide nicotine slowly without any immediate feedback or sensorimotor reinforcement. Interestingly, pregnant smokers seem to experience more severe cigarette withdrawal and cravings than other adults [34]. This could be related to stress and/or metabolic changes in pregnancy. Finally, pregnant women metabolise nicotine faster than other smokers and may need higher nicotine doses delivered at a faster rate than standard NRT formulations provide [35].

In contrast to NRT products, EC provide a degree of sensori-motor replacement for smoking and a degree of enjoyment [18]. They also allow extensive individualisation (of flavour, ease of use, and other product characteristics). Regarding nicotine delivery, EC remain inferior to cigarettes, but they deliver nicotine faster than nicotine patches and oral NRT products [36] and unlike patches, they allow for titration of nicotine intake to smokers' needs. These characteristics make it likely that pregnant smokers will adhere to EC treatment much better than to NRT treatment, possibly even magnifying this effect observed with other smokers (in the randomised trial comparing patches and EC, adherence to EC was over three times higher than adherence to patches – [19]). Pregnant smokers using EC are also likely to obtain more adequate nicotine replacement levels and withdrawal relief.

Despite being more palatable than NRT and providing better nicotine replacement, EC deliver lower levels of nicotine than cigarettes, do it much more slowly, and do not include other chemicals contributing to the addictiveness of cigarettes. Even enthusiastic EC users report much lower levels of dependence on EC than they experienced with cigarettes [37]. The National Centre for Smoking Cessation Training (NCSCT) midwifery guidance considers vaping (EC use) in pregnancy better than smoking [38].

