10.2 Secondary Objective/s

To assess safety of electronic cigarettes (EC) compared to safety of nicotine transdermal patches when used to help pregnant smokers stop smoking; to assess effects of the two interventions on changes in smoke intake and in nicotine intake, effects on short-term abstinence; and adherence to each treatment.

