10.5 Objectives and End Points Summary

Primary Objective	Primary Endpoint	Outcome Measures
Efficacy of EC compared to	Abstinence rates in each	Prolonged abstinence at end of
NRT	group at end of	pregnancy from 2 weeks post-
	pregnancy	TQD defined as per Russell
		Standard abstinence criteria,
		biochemically validated
Secondary Objectives	Secondary Endpoints	Outcome Measures
Effects on Smoke and	Change in smoke and	Salivary cotinine and anabasine
Nicotine intake from EC and	nicotine intake from	
NRT users; 'dual users'; and	baseline to end of	
reducers (50% or more)	pregnancy	
Efficacy of EC compared to	Abstinence at 4 weeks	Self-reported point prevalence
NRT	post-TQD, end of	abstinence (not a puff over the
	pregnancy, and 3-	previous week) at 4 weeks post-
	months post-partum.	TQD, at end of pregnancy and at 3
		months post-partum; self-
		reported prolonged abstinence at
		end of pregnancy and at 3-
		months post-partum
Treatment adherence	Use of EC and NRT	Self-reported EC and NRT use
		(number of days used; amount
		and products used; product
		changes)
Safety of EC compared to	Adverse events	Self-reported adverse events and
NRT	throughout the	SAE's
	intervention period and	
	at 3 months post-	SAE's identified at 3-months post-
	partum (for both	partum follow-up calls.
	mother and infant).	
	Birth and maternal	Birth and maternal outcomes:
	outcomes	Birth weight; gestational age; C-
		section delivery; still
		birth/miscarriage/neonatal or
		post-neonatal death; maternal
		death; neonatal intensive care
		admission

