12.8 Trial Schedule

12.8.1 Schedule of Treatment for each visit

The following data will be collected and interventions delivered:

Baseline visit:

Demographic information, smoking history including whether participants live with other smokers, cigarettes smoked per day (cpd), nicotine dependence, previous stop smoking attempts and medication use, saliva sample to assess anabasine and cotinine levels to measure baseline smoke and nicotine intake, contact details of family and friends (to assist with follow ups where participants' contact details change).

Following randomization, a member of the research team will demonstrate how to use the allocated product. Further details on each intervention are described next. The research team will also arrange a suitable time for the first call from the stop-smoking advisor.

Once participants are randomised into the trial and the local PI confirms eligibility, the participants will be under the care of the local PI and staff at the trial co-ordinating centre, (HAL, QMUL).

Intervention details:

The initial and further supplies of patches or EC will be by mail, accompanied by behavioural support over the telephone.

Nicotine Patch: The study will use 15mg/16hr nicotine patch or 10mg/16hr for smokers who find the former too strong. They will be advised to wear one patch a day during waking hours as per its medicinal license. Medication will be posted form the QM main site. This is an open label RCT where the nicotine patches, a product available OTC, are being used within their medicinal licensing and so there are no special labelling or packaging requirements. The medication will be stored at the site in facilities that meet the requirements of GCP. The facilities for storage of the medication will be checked to ensure that the drug will remain stable and will be stored securely. The researcher will dispense the medication in accord with the protocol and will record the batch numbers on a log. Each person will be dispensed 2-week supply of patches initially and offered further supplies over the phone for up to 8 weeks. Patches will be sent via recorded delivery.

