Smoking status; use of EC, NRT and any other stop smoking medications; adverse events. We will also collect birth and maternal outcomes with the prior consent of participants (date of birth, birthweight, gestational age, still births, miscarriage, maternal death, congenital abnormalities, neonatal and post-neonatal deaths, neonatal intensive care admission and delivery by C-section) from hospital records. Participants reporting abstinence from smoking, reduction of cigarette consumption of 50% or more, and those smoking and using NRT or EC, will be asked to provide saliva samples for cotinine and anabasine analysis. Sampling kits will be sent by post together with instructions, and self-addressed envelope for sample return. A visit will be offered if postal samples are not returned. Participants will be provide with £20 for their time in returning the saliva sample. The cut off points for classifying participants as abstainers will be cotinine < 15 ng/ml [42] for those not reporting using any nicotine product and anabasine< 1 ng/ml [43] for those reporting any NRT/EC use.

Three months post-partum phone call

Participants will be contacted to check on any adverse events to themselves or their infant since end of pregnancy, and to record smoking status and product use.

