17.6 Secondary outcome analysis

Secondary and safety outcomes will also be analysed on an intention to treat basis where possible. Binary outcomes including self-reported quit rates at 4 weeks post-quit and at end of pregnancy, and 7-day point-prevalence abstinence will be analysed by logistic regression and continuous outcomes, including birthweight and gestational age by multiple linear regression. In infant outcomes analysis we will allow for clustering in multiple births.

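### The saliva-marker endpoint is confined to groups formed after randomisation, so it should be labelled descriptive: a between-arm comparison within them would not be a randomised one

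*Protocol*

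**What the plan says.** Protocol section 10.2 sets the secondary objective "to assess effects of the two interventions on changes in smoke intake and in nicotine intake". Section 10.3.2 has the corresponding markers, salivary anabasine and cotinine, "assessed for participants still using NRT or EC at end of pregnancy". The same sentence then adds two further groups with the words "and for 'dual users' or those who have reduced their smoking by 50% or more". The summary table in section 10.5 names the same three groups and gives the endpoint as change from baseline to end of pregnancy.

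Sampling is wider than the endpoint in one respect and incomplete in another. At baseline, section 12.8.1 schedules a "saliva sample to assess anabasine and cotinine levels to measure baseline smoke and nicotine intake". At end of pregnancy it asks for saliva from "Participants reporting abstinence from smoking, reduction of cigarette consumption of 50% or more, and those smoking and using NRT or EC". Abstainers are therefore sampled whether or not they use a product. Women who still smoke, have not halved their consumption and use no product are not.

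On analysis, section 17.6 says "Secondary and safety outcomes will also be analysed on an intention to treat basis where possible" and sends continuous outcomes to multiple linear regression, giving birthweight and gestational age as examples. Section 17.9 makes all randomised participants the analysed population.

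**The concern.** Product use, dual use and halving of consumption at end of pregnancy are all determined after allocation. The third is a version of the outcome being measured. If treatment changes who falls into these groups, the two arms' subsets are no longer comparable, even though the arms were.

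The protocol gives its own reason to expect that. Section 8.1 reports that "in the randomised trial comparing patches and EC, adherence to EC was over three times higher than adherence to patches", and that only 7% of women in the large UK patch trial used patches beyond one month. More EC-arm women are then likely to enter the subset simply because they still use the product, including women whose smoking has hardly changed. Similar women in the patch arm, off product, drop out of it. A contrast of the two subset means could show a difference in smoke intake where there is none, or hide or invert a real one.

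**Working it through.** **The plan's own figure.** The protocol gives no sample size or power for this endpoint. Its only calculation is for the primary endpoint, 8% v 14%, and that reproduces: n per arm = [1.96·√(2 × 0.11 × 0.89) + 1.2816·√(0.08 × 0.92 + 0.14 × 0.86)]² / 0.06² ≈ 569.4, so 570 per arm and 1,140 in total. Nothing below touches it.

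**Method.** Subset mean = Σ(share × proportion included × change) / Σ(share × proportion included). All figures are for smoke intake (anabasine) only.

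**Illustration 1: identical smoking in both arms. All inputs are assumed.**
- In each arm: 10% abstinent (change −100%), 30% reducers (−60%), 60% unchanged (0%).
- All randomised: 0.10 × (−100) + 0.30 × (−60) = −28% in both arms, so the true difference is 0.
- Product use in the patch arm: 5% of abstainers and 5% of unchanged smokers.
- Product use in the EC arm: 60% of abstainers, and 50% (larger case) or 20% (milder case) of unchanged smokers.
- Reducers are included by definition.

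If off-product abstainers are not counted as reducers:
- Patch: (−0.5 − 18) / (0.005 + 0.30 + 0.03) = −18.5 / 0.335 = −55.2%
- EC, larger case: (−6 − 18) / (0.06 + 0.30 + 0.30) = −24 / 0.66 = −36.4%, a false 19 points against EC
- EC, milder case: −24 / (0.06 + 0.30 + 0.12) = −24 / 0.48 = −50.0%, a false 5 points against EC

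If off-product abstainers are counted as reducers:
- Patch: −28 / (0.10 + 0.30 + 0.03) = −28 / 0.43 = −65.1%
- EC, larger case: −28 / 0.70 = −40.0%, a false 25 points
- EC, milder case: −28 / 0.52 = −53.8%, a false 11 points

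The direction also depends on the inputs. On the first reading, if only 5% of unchanged EC-arm smokers used a product, the EC mean would be −24 / (0.06 + 0.30 + 0.03) = −24 / 0.39 = −61.5%, a false 6 points in favour of EC.

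**Illustration 2: inputs closer to the protocol.** The quit rates of 8% and 14% come from section 17.1. Patch use of 7% borrows the beyond-one-month figure in section 8.1; EC use of 21% is three times that, with 40% as an assumed upper case. Also assumed: 25% reducers with a mean cut of 70%, the rest with a mean cut of 15%, and product use independent of smoking. Results are mean reductions, with off-product abstainers not counted as reducers.

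| Scenario | All randomised, patch v EC | Subset, patch v EC |
|---|---|---|
| 8% quit in both arms, EC use 21% | 35.6 v 35.6 | 62.0 v 52.3 (about −10) |
| 8% quit in both arms, EC use 40% | 35.6 v 35.6 | 62.0 v 45.0 (about −17) |
| 8% v 14% quit, EC use 21% | 35.6 v 40.7 (+5.1) | 62.0 v 54.9 (−7.2) |
| 8% v 14% quit, EC use 40% | 35.6 v 40.7 (+5.1) | 62.0 v 48.7 (−13.4) |

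For example, patch: (0.08 × 0.07 × 100 + 0.25 × 70 + 0.67 × 0.07 × 15) / (0.0056 + 0.25 + 0.0469) = 18.76 / 0.3025 = 62.0. EC in the third row: (0.14 × 0.21 × 100 + 0.25 × 70 + 0.61 × 0.21 × 15) / (0.0294 + 0.25 + 0.1281) = 22.36 / 0.4075 = 54.9. In the last two rows a real benefit of EC appears with the wrong sign.

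**The case against.** The strongest reply is that the protocol never specifies a between-arm test here. In section 10.5 the efficacy and safety rows set EC against NRT, whereas the intake row speaks only of intake in users, dual users and reducers, and of change from baseline. Section 17.6 names no model for the saliva markers, and its intention-to-treat promise is qualified. The SAP, not at hand, may treat the results as descriptive, and within-person change in these groups is a legitimate description. Much of this stands. A reader might infer that the protocol commits the trial to a biased test, or that the endpoint has no value; the text supports neither. What remains is that section 10.2 frames the endpoint as an effect of the interventions, section 17.6 sends continuous outcomes to regression, and nothing marks this one as an exception.

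Three further limits also stand:
- A reader might take it that off-product abstainers are excluded. The text does not settle this: a woman who has stopped has literally cut by more than half, yet section 12.8.1 lists abstainers and reducers separately. Counting them in does not remove the artefact; on the illustration's inputs it is larger.
- The 19-point figure should not be read as an estimate. It needs EC use 10 to 12 times patch use, and the protocol's own indication is a little over threefold, from a trial in other smokers.
- A change of −100% in abstainers cannot apply to cotinine in women still taking nicotine. No size is offered for nicotine intake.

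**Conclusion.** The point holds in this form: the three groups are defined after randomisation, one of them by the outcome, and the protocol expects product use to differ by arm. Any between-arm contrast of anabasine or cotinine within them is therefore not a randomised comparison and could be biased or change sign. This follows from the definitions and needs no assumed numbers.

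The size does rest on assumptions. With identical smoking in both arms, Illustration 1 gives a false difference in smoke intake of about 5 to 19 points against EC, or 11 to 25 points if off-product abstainers count as reducers. Illustration 2 gives a similar range and shows that a true advantage of about 5 points can be reversed. Actual product use at end of pregnancy is unknown. Supplies in both arms stop at 8 weeks, and the endpoint counts any NRT or EC, not only the allocated product.

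This is one secondary endpoint. It should be put right, but the primary endpoint and the sample size of 1,140 are not affected.

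**What to change.** In sections 10.2, 10.3.2, 10.5 and 17.6, state that the anabasine and cotinine results in product users, dual users and reducers are within-group descriptions of change from baseline, shown by arm, with no between-arm test and no claim of a treatment effect. State also whether abstainers no longer using a product, who are already sampled under section 12.8.1, belong to the reported groups.

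If an all-randomised comparison is wanted, present it as supportive only. State the assumption made for unsampled continuing smokers and vary it, for example baseline carried forward against alternatives. Carrying baseline forward should not be the sole analysis, because whether a continuing smoker is measured or imputed would then itself depend on product use. The protocol's rule that missing means smoking classifies a yes/no status; it does not supply a marker value.

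The cost is a wording change with no extra samples. The downside is that the trial gives up a formal between-arm claim on this secondary endpoint. Recovering a measured comparison would require end-of-pregnancy saliva from every woman reached, and so additional resources.

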9.0 Trial Flowchart

The research team and routine care staff will identify potential participants and provide them with study information and an appointment for the screening and randomisation visit, which can coincide with routine hospital visits.

Screening and randomisation visit with the research team

Informed consent, baseline data, estimated date of delivery and saliva samples will be collected. Women will be randomised to use either nicotine patches or EC. The research team will explain the allocated treatment and will then set a day and time for the participant to receive their first call by the stop smoking advisor.

Experimental Group (n=570)

Queen Mary (QM) team will post: an EC starter-kit and the initial 2 week supply of e-liquid with instructions on use

Phone calls pre-TQD, on TQD, 1, 2, 3 and 4 weeks post-TQD by QM team

smoking status

behavioural support including setting a target quit date (TQD), advice on coping with withdrawal discomfort and tempting situations

monitoring EC and any other treatment use adverse events

further EC supplies posted as needed

At end of pregnancy (35 weeks-10 weeks post-partum)

by QM team:

participants contacted by telephone smoking status

EC and any other treatment use

adverse events

saliva samples for anabasine and cotinine analysis (if abstinent, 'dual-user' or reduced smoking by 50%) provided via mail

by research team: birth and maternal outcomes

3 months post-partum by QM team

Participants contacted by telephone to report any serious adverse events (mother and baby) since delivery and their smoking status.

Control Group (n=570)

QM team will post:

an initial 2 week supply of 15mg/16hr nicotine patches with instructions on use

Phone calls pre-TQD on TQD, 1, 2, 3 and 4 weeks post-TQD by QM team

smoking status

behavioural support including setting a TQD, advice on coping with withdrawal discomfort and tempting situations

monitoring patch and any other treatment use adverse events

further patch supplies posted as needed

At end of pregnancy (35 weeks-10 weeks post-partum) by QM team

by QM team:

participants contacted by telephone smoking status

EC and any other treatment use

adverse events

saliva samples for anabasine and cotinine analysis (if abstinent, 'dual-user' or reduced smoking by 50%) provided via mail

by research team: birth and maternal outcomes

3 months post-partum by QM team

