10.7 Study Setting

Participants will be recruited by maternity services at sites across England, and by Stop Smoking Service in Scotland. We plan to include at least 23 recruiting sites across England and 1 site in Scotland, and have a further 6 sites in England, and 2 sites in Scotland as reserve sites, in case of slow recruitment rates. Queen Mary University of London is a non-recruiting, Non NHS Site, acting as the coordinating centre and performing intervention delivery, data collection and follow up telephone calls.

In England, Clinical Research Networks (CLRN) research midwives (RM) and routine care staff will recruit potential participants. In some sites RM may not be routinely available, but other relevant staff (such as clinical trial associates or research nurses) would be trained to carry out the research procedures. Those not eligible to take part in the study but interested in obtaining help with stopping smoking will be referred to local stop smoking services as per standard practice.

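### End-of-pregnancy 7-day point prevalence is self-report only, although saliva is requested at that contact from every woman reporting abstinence; a validated version should be added (minor)

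*Protocol*

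**What the plan says.** Protocol section 10.3.2 lists "7-day point-prevalence abstinence self-reported at 4 weeks, end of pregnancy and at 3 months post-partum" among the secondary endpoints. The summary table in section 10.5 repeats the definition ("Self-reported point prevalence" abstinence, meaning no puff in the past week). Section 17.6 puts "self-reported quit rates at 4 weeks post-quit and at end of pregnancy, and 7-day point-prevalence abstinence" into logistic regression and mentions no validated form. Biochemical validation is attached only to prolonged abstinence, the primary endpoint (10.3.1, 10.5, 17.5).

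At the end-of-pregnancy contact, section 12.8.1 requests saliva, to be assayed for both markers, from three groups: "Participants reporting abstinence from smoking, reduction of cigarette consumption of 50% or more, and those smoking and using NRT or EC". The flowchart in section 9.0 has the same rule: "saliva samples for anabasine and cotinine analysis (if abstinent, 'dual-user' or reduced smoking by 50%) provided via mail". A visit is offered when the postal sample does not come back (12.8.1), and all samples are analysed before the end-of-study notification (13.7). The cut-offs are cotinine below 15 ng/ml for women reporting no nicotine product and anabasine below 1 ng/ml for those using NRT or EC.

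The trial is open label (12.8.1). The coordinating centre is described in section 10.7 as "performing intervention delivery, data collection and follow up telephone calls". The schedule in section 12.8.2 has no saliva sample at 4 weeks or at 3 months post-partum.

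**The concern.** Self-reported abstinence is open to over-claiming. The women here know their allocation, and follow-up calls come mostly from the centre that supplied the product and the counselling, so over-claiming could differ between arms. If it does, a self-reported endpoint can show a difference that does not exist or hide one that does. If it is equal, a real effect is diluted.

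The protocol has five secondary abstinence measures: point prevalence at three time points and prolonged abstinence at two. All five are self-report. For end-of-pregnancy point prevalence the validating sample is already requested from every woman who would count as abstinent, and a single sample is well suited to checking current status. As written, a woman whose saliva fails the cut-off is a smoker for the primary endpoint but stays an abstainer for point prevalence at the same contact. Point prevalence is also the measure that captures women who stopped later than two weeks after the quit date and were smoke-free at the end of pregnancy.

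**Working it through.** **1. The protocol's own sample size (17.1).** Inputs: 8% v 14%, two-sided alpha 0.05, power 90%. With the pooled-variance formula:

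n per arm = [1.960 × √(2 × 0.11 × 0.89) + 1.282 × √(0.08 × 0.92 + 0.14 × 0.86)]² / 0.06² = (0.867 + 0.564)² / 0.0036 ≈ 569.4, rounded up to 570, or 1,140 in total.

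This matches the stated figure. It concerns the primary endpoint; the protocol states no power for point prevalence. The expected primary events are 0.08 × 570 ≈ 46 and 0.14 × 570 ≈ 80.

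**2. Over-claiming that differs by arm.** Assumptions not in the documents: true point prevalence 20% in both arms (30% as an alternative), and over-claiming d points higher in one arm. With 570 per arm:

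SE = √(2 × 0.20 × 0.80 / 570) = 2.37 points; at 30%, √(2 × 0.30 × 0.70 / 570) = 2.71 points.

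Probability of a significant result = Φ(−1.96 + d/SE) + Φ(−1.96 − d/SE).

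| d (points) | 20% prevalence | 30% prevalence |
|---|---|---|
| 0 | 5% | 5% |
| 1 | 7.1% | 6.6% |
| 2 | 13.5% | 11.4% |
| 3 | 24.5% | 19.7% |

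**3. A second parametrisation.** Let f be the share of non-abstinent women who claim abstinence, so the observed rate is p + (1 − p)f. Borrow p = 8% in both arms from the primary endpoint.

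- f = 5% v 7.5%: observed 12.6% v 14.9%; a false significant result in favour of the arm that over-claims more about 20% of the time.
- f = 5% v 10%: observed 12.6% v 17.2%; about 59%.

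Reversing the arms in the 5% v 10% case reverses the direction with the same 59%.

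**4. Equal over-claiming.** With true rates of 8% v 14%:

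- f = 5% in both: 0.08 + 0.92 × 0.05 = 12.6% and 0.14 + 0.86 × 0.05 = 18.3%; the risk ratio falls from 1.75 to 1.45 and power from 90% to 76%.
- f = 10% in both: 17.2% and 22.6%; risk ratio 1.31, power 63%.

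If the true rates are equal, equal over-claiming leaves the false-positive rate at 5%.

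**5. What validation would need.** Saliva is requested from all women reporting abstinence (9.0, 12.8.1), all samples are analysed (13.7) and the cut-offs exist (12.8.1). No further sample request or assay is needed, and the sample size stays at 1,140.

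**The case against.** The text does not contradict itself: sections 10.3.2 and 10.5 agree and openly label the measure as self-report. Abstinence at this time point is validated, for the primary endpoint, so the main conclusion is protected. The SAP is not among the documents and could add a validated version. This stands, and it limits the point to an improvement. It does not remove it, because the protocol itself fixes the endpoint definition.

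Several stronger readings are tempting and are not supported:

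- A reader might infer that saliva results will exist for every woman claiming abstinence. Samples are requested, mostly by post, and some will not come back.
- A reader might infer that validation is free of any drawback. Counting no sample as smoking misclassifies some true abstainers, and it can itself bias the comparison if return differs by arm.
- A reader might infer that only a validated version would avoid recall of lapses over months. The existing 7-day measure does not rely on long recall either. Validation guards against misreporting.
- A reader might infer that the primary will yield too few events and that the secondary endpoints will carry the interpretation. About 46 v 80 expected events at 90% power do not suggest this.
- A reader might take the cut-offs in section 12.8.1, which are given for classifying abstainers without naming an endpoint, as already covering point prevalence. Sections 10.3.2 and 10.5 explicitly say self-report.

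Three practical objections also stand. Contact may run to ten weeks post-partum (10.3.1), so a late sample reflects smoking at that time and not before delivery. Local teams may collect some follow-up answers (12.8.4), so reports do not always go to the coordinating centre. And the change covers one of the five self-reported measures; the others stay exposed.

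**Conclusion.** The point holds as a cheap improvement of minor severity. End-of-pregnancy 7-day point prevalence is self-report only, in an open-label trial that already plans to request the validating sample from each woman reporting abstinence. No secondary abstinence measure is therefore protected against over-claiming that differs by arm. The validated primary endpoint and its power are unaffected.

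The size depends wholly on assumed inputs. At 20% true prevalence, a 1 to 3 point difference in over-claiming gives a false-positive rate of about 7% to 25%; the alternative parametrisation gives 20% to 59%. The documents give neither the rates nor a direction, so these figures show sensitivity and are not a forecast of bias.

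**What to change.** In Protocol sections 10.3.2, 10.5 and 17.6, before outcome data are seen:

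- Add biochemically validated 7-day point-prevalence abstinence at end of pregnancy, with the primary's cotinine and anabasine cut-offs and no sample counted as smoking. Report it alongside the self-reported version.
- Report sample return by arm among women claiming abstinence.
- State that a sample taken after delivery validates status at sampling and not status before delivery, and add a sensitivity analysis restricted to pre-delivery contacts. Samples carry their collection date (13.3) and the date of birth is recorded (12.8.1), so samples taken before delivery can be identified.
- Leave the 4-week and 3-month post-partum measures as self-report, labelled as such.

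The cost is endpoint wording, one extra regression and the sensitivity analysis; no extra sample, assay or participant. The downside is a lower reported rate, because some true abstainers will not return a sample, and possible bias if return differs by arm. That is why both versions should be reported.
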